### ***8.6 Study Halting Rules***

Use of subject device will be halted when three grade 3 AEs determined to be “probably related” are reported to the, [name]. [name] will notify the study sponsor and investigators immediately when the third grade 3 event is reported and enrollment screens will stop accepting new study participants. The study sponsor will inform the DSMB members within 24 hours of this occurrence and will provide the DSMB with AE listing reports. The DSMB will convene an ad hoc meeting by teleconference or in writing as soon as possible. The DSMB will provide recommendations for proceeding with the study to the study sponsor.

### ***8.7 Safety Oversight***

Data Safety Monitoring will be conducted by [name], who is a board-certified gastroenterologist trained in endoscopic procedures including upper endoscopy. Data safety monitoring will be done after each cohort of 10 patients is enrolled.

SAE and AE are defined as:

- Aspiration of the capsule on ingestion  
Immediate identification through extensive coughing. Localization and retrieval with bronchoscope.
- Delayed excretion, or failure to excrete the capsule (capsule retention)  
Identification
- Obstruction of the digestive tract

- Injury to tissue structures during the passage of the HemoPill acute through the digestive tract. In particular, this may involve:
  - Injury to the mucosa
  - Bleeding, e.g., variceal bleeding
  - Perforations

Furthermore, unexpected events are classified as SAE or AE under consideration of the respective definitions provided in chapter 8.1.1 and chapter 8.1.2

## 9 Clinical Trial Monitoring

Clinical site monitoring is conducted to ensure that the rights and well-being of human subjects are protected, that the reported trial data are accurate, complete, and verifiable, and that the conduct of the trial is in compliance with the currently approved protocol/amendment(s), with GCP, and with applicable regulatory requirement(s).

The PI will monitor the study. In addition to completed medical records, the procedure report, and any additional supporting documents will be made available for review and verification during each monitoring visit.

Study monitoring will be conducted routinely throughout the study. The monitors will confirm that the study is being conducted according to the protocol.

## 10 Statistical Considerations

### 10.1 Statistical and Analytical Plans (SAP)

No additional formal SAP is provided.

### 10.2 Statistical Hypotheses

Formal hypotheses are only specified for the primary clinical effectiveness endpoint, the detection of blood in the gastrointestinal lumen with both measurements.

The assumed null hypothesis is that the accuracy of the HemoPill acute measurement in comparison with endoscopic finding is 50%, equaling a random distribution and no relation between these measurements. As the alternative hypothesis, it is assumed that the accuracy is equal or higher to 75%. This concrete accuracy value is derived from previous results of Brunk et al. (2021), see section 2.1.

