### **Telemetric capsule-based upper gastrointestinal tract – blood detection – first multicentric experience**

Brunk and colleagues presented results from an observational study on the use of the HemoPill in terms of safety and usability under real-life conditions from experiences in 12 hospitals (Brunk T et al., 2021). The use of the HemoPill in 61 patients was retrospectively analyzed. Indications for HemoPill application were clinical suspicion of UGIB, suspected small bowel bleeding after uneventful esophagoduodenoscopy (EGB) and colonoscopy if symptoms persisted, or exclusion of rebleeding after hemostasis. Primary endpoints were technical success and bleeding detection/exclusion. Secondary endpoints included adverse events and change of clinical course. Complete baseline characteristics were available in 49 of 61 patients (80.3 %). Mean age was 70 ( $\pm$  10.7) years, 41 % were female. Mean hemoglobin level at admission to the emergency department was 8.1 g/dL ( $\pm$  1.6). Over signs of bleeding such as melaena and/or hematochezia were present in 27 patients (55 %). Median Glasgow-Blatchford score (GBS) was 10 (range 0 – 19). 46 patients (94 %) had a GBS > 1. 61 patients received the HemoPill; in 45 patients (74 %), the capsule was administered due to the suspicion of UGIB, in 12 patients (20 %), the capsule was used for detection of a suspected small intestinal bleeding and in 4 patients (7 %), HemoPill was used as a “second look” tool after primary hemostasis in the upper GI-tract. One patient was excluded as data transfer was stopped after 10 minutes of recording. Of the remaining 60 patients, 35 (58 %) had a positive capsule signal while 25 (42 %) had a negative HemoPill result. In 20 of 35 patients (57 %) with a positive HemoPill signal, evidence of bleeding was seen in a subsequent endoscopic work up. The bleeding sources were angiodysplasia (n = 10), peptic ulcer (n = 5), Dieulafoy lesion (n = 1), esophageal varices (n = 1), esophagitis (n = 1), erosive gastritis (n = 1), unknown as only blood was seen (n = 1). In 15 of 35 patients with a positive HemoPill signal, no bleeding source was detected, yet only in 11 of these 15 patients an EGD was performed.

In 20 of 25 HemoPill negative patients, endoscopy was performed and did not reveal a bleeding source or blood/hematin. Until discharge, no clinically relevant bleeding was detected in HemoPill negative patients.

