## 2.2.5 Clinical Data to Date

Publications of clinical data on the use of HemoPill in Europe is described in chapter 2.1. Prior to market entry in the EU, a clinical trial was conducted which is described in the following:

Ovesco conducted a prospective non-randomized, single-center, open-label study to investigate feasibility and safety of the HemoPill acute in patients with symptoms of UGIB. The primary aim of the study was to investigate feasibility and safety of the device in a clinical setting. All patients underwent endoscopy within 12 hours after capsule ingestion. Sensor data from the capsule within 10 minutes after ingestion were compared with endoscopic findings.

From April 2015 to February 2016, 30 consecutive patients with symptoms of acute UGIB were included.

Objective and clinical endpoints of the investigation were:

- Safety of the capsule
- Feasibility of bleeding detection
- Evaluation of threshold values for the sensor capsule data
- Sensitivity and specificity of the sensor capsule data

The clinical investigation population were patients with indications on esophagogastroduodenoscopy (ESG) and with suspected upper GI bleeding. Inclusion criteria were:

- Clinical suspicion based on anamnestic statements of clinical symptoms such as hematemesis, tarry stools/melena
- Alert and conscious patient
- Written informed consent
- Age  $\geq$  18 years and  $\leq$  80 years.

The capsule was swallowed by the patient and an external study receiver recorded the capsule sensor data for 4 consecutive hours. Patients underwent endoscopy within 12 hours after capsule ingestion. Afterwards, the endoscopic findings (endoscopy pictures and patient's endoscopy record) were compared to the sensor capsule data results. Capsule excretion was monitored for up to 4 days. If excretion was not recorded during that time, a follow up examination of the patient would have been conducted after 10 days.

30 consecutive patients with symptoms of acute UGIB were included; 28 were eligible for analysis. All together the HemoPill acute was found to be feasible and safe.

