## 10.4 Description of Statistical Methods

### 10.4.1 General Approach

This study has a double blinded, prospective diagnostic case-control design. This prototypic design of diagnostic accuracy study is a consecutive series of individuals in whom the target condition is suspected, here GI lumen bleeding. The index test, here HemoPill acute, is performed first in all participants. Subsequently, the presence of the target condition is also measured in all participants with the reference standard, in this case endoscopy (Rutjes et al. 2005).

In more detail, this study is performed:

- on one sample: the study is conducted on a single sample (single-arm) at a single center
- double blinded: neither the patients nor the investigators are aware of the result of the subjective device, the HemoPill acute capsule, during the examination of the control product, the endoscopy.
- with repeated measurement: all patients are measured with the subjective device and additionally with the control product
- case-control design: the status of a patient with positive endoscopy result equals as classification in the case group, the status of a patient with negative endoscopy result equals as classification in the control group. This classification is determined after the study process, during the statistical analysis to ensure double blindness.

The categorical variables (such as positive or negative test results) will be summarized with subject counts, respectively frequency, and percentages.

As inferential test a  $\chi^2$  test, goodness-of-fit test of a 2 x 2 contingency table with two tailed p-value of  $\alpha \leq .05$  will be used.

The assumption of the  $\chi^2$  test, goodness-of-fit test, a required minimal expected cell size of 5, will be controlled (and is a priori controlled in the power analysis, see section 10.5). The dichotomous data level of the two factors, results of subjective device and results of control product, are transformed into a cell count, observed cases, in the 2 x 2 contingency table.

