### 10.4.2 Analysis of the Primary Efficacy Endpoint(s)

The original continues data level of the subject device, HemoPill acute, the so-called HI-value, is transformed during the study process by the investigator in dichotomous values, negative or positive for GI lumen bleeding, i.e. negative or positive output results (described in detail in section 2.1.2.2).

The qualitative visual data of the control product, the endoscopy, is also transformed during the study process by the investigator in dichotomous values, negative or positive for GI lumen bleeding, i.e. negative or positive output results (described in section 4.1).

After the study process the values of these two factors (HemoPill acute: negative or positive, endoscopy: negative or positive) are combined in a 2 x 2 contingency table with four possible results:

- True positive: HemoPill acute measurement positive; Endoscopy measurement positive
- False positive: HemoPill acute measurement positive; Endoscopy measurement negative
- True negative: HemoPill acute measurement negative; Endoscopy measurement negative
- False negative: HemoPill acute measurement negative; Endoscopy measurement positive

(for detailed description see section 4.1)

From this 2 x 2 contingency table the summary three test indices are calculated accuracy (ACC, = (TP + TN) / pop), sensitivity (true positive rate) and specificity (true negative rate).

The significance of these results will be analyzed using the  $\chi^2$  test, goodness-of-fit test of a 2 x 2 contingency table with two tailed p-value of  $\alpha \leq .05$ .

The data assumption of the  $\chi^2$  test, goodness-of-fit test, a required minimal expected cell size of 5, will be controlled. After the inference analysis the 95% confidence intervals of the test indices can be calculated. If either of both measurement results is missing for a patient, the whole subject is omitted from the data analysis.

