## 10.5 Sample Size

The study will enroll in total n = 50 participants:

- at least 43 eligible for statistical analyses
- plus 7 as highest expectable dropout count.

The required sample size of n = 43 was calculated for the planned  $\chi^2$  test for the test indices (accuracy, sensitivity and specificity). The calculation was based on the previous clinical study of Burk et al. (2021) which provide an accuracy of 75% (sensitivity of 100% and specificity of 63%) equaling an assumed effect size  $w = 0.62$ . The calculation was done with an a priori set  $\alpha$  error of .05 and a targeted power (1- $\beta$ ) equal or higher than .90.

Based on the previous studies dropout ratios between 2% (Burk et al., 2021) and 7% (Caca & Zimmermann, 2017) could be expected. By reason of clinical judgement, a maximal dropout ratio of 14% was assumed (which equals two times the maximal previous dropout ratio). An assumed maximal dropout of 14% equals 7 additional participants (when targeting at least 43 participants eligible for statistical analyses).

The targeted n = 43 also assures the required minimal expected cell size of 5 for a  $\chi^2$  test being applicable. The method of power analysis was an a priori required sample size computation with given  $\alpha$ , power and effect size. The power analysis was conducted with the computer program G\*Power 3.1 (Faul et al., 2009).

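### Section 10.2 equates 50% accuracy with no relation, the goodness-of-fit test has no stated null proportions or df, and w = 0.62 does not give n = 43 for any 2 x 2 test, although 43 is right for accuracy 75% vs 50%

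*Combined protocol and SAP*

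**What the plan says.** Section 10.2 (Statistical Hypotheses) puts the null at an accuracy for which "endoscopic finding is 50%, equaling a random distribution and no relation between these measurements", and the alternative at 75% or more. Section 10.1 states: "No additional formal SAP is provided".

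Section 10.4.1 names the inferential test as a chi-square "goodness-of-fit test of a 2 x 2 contingency table with two tailed p-value of" .05. Section 10.4.2 applies it to accuracy, sensitivity and specificity together and adds that afterwards "the 95% confidence intervals of the test indices can be calculated". Neither section gives expected proportions or degrees of freedom.

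Section 10.5 says: "The required sample size of n = 43 was calculated for the planned" chi-square test of those three indices. It relies on a previous study said to "provide an accuracy of 75% (sensitivity of 100% and specificity of 63%) equaling an assumed effect size" w = 0.62, with alpha .05 and power of at least .90. Seven further patients for dropout bring enrolment to 50.

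The counts behind the 75% are in section 2.1: of 60 patients, "35 (58 %) had a positive capsule signal while 25 (42 %) had a negative HemoPill result". Bleeding was confirmed in 20 of the 35 positives and in none of the negatives. Sections 3.1 and 4.2.1 make the clinical relation between capsule and endoscopy the primary objective and endpoint.

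**The concern.** Three statements that should describe one test do not fit together. The null is a value of accuracy, but it is explained as absence of a relation, which is a different hypothesis. The test is named but its null distribution is not given. The effect size does not lead to the stated sample size.

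Two things are at stake. With the expected proportions unstated, the choice between several non-equivalent tests could be made after the data are seen. And if few patients bleed and the capsule is seldom positive, accuracy above 50% can arise from those shares alone and still be reported as the relation that the trial set out to show.

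**Working it through.** **1. The plan's own figure.** Inputs from section 10.5: alpha .05, power .90, w = 0.62, n = 43. For a chi-square test N = lambda / w², where lambda is the noncentrality that gives 90% power.

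| df | lambda | N at w = 0.62 (w² = 0.3844) | N at w = 0.50 (w² = 0.25) |
|---|---|---|---|
| 1 | 10.51 | 27.3, so 28 | 42.03, so **43** |
| 2 | 12.65 | 32.9, so 33 | 50.6, so 51 |
| 3 | 14.17 | 36.9, so 37 | 56.7, so 57 |
| 5 | 16.47 | 42.8, so 43 | 65.9, so 66 |

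The section 10.2 hypotheses, taken as correct versus incorrect at 75/25 against 50/50, give w = √(0.25²/0.5 + 0.25²/0.5) = 0.50 with 1 df. That reproduces 43 exactly (power 0.906; 0.8998 at 42). The dropout step also holds: 43 / 0.86 = 50. The stated w = 0.62 reaches 43 only at 5 df, which no test of a 2 x 2 table has.

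**2. What 0.62 matches.** Section 2.1 gives TP 20, FP 15, TN 25, FN 0 (n = 60): accuracy 45/60 = 75%, specificity 25/40 = 62.5%. Against four equal cells, w = √[(0.0833² + 0² + 0.1667² + 0.25²) / 0.25] = √0.3889 = 0.624. Against independence it is 0.598.

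**3. Accuracy when there is no relation.** With endoscopy-positive share p and capsule-positive share q, expected accuracy is pq + (1 − p)(1 − q). This is 50% only if p or q is 50%.

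- Cited series, p = 20/60 and q = 35/60: 0.194 + 0.278 = 47.2%. Section 2.1 implies that only 51 of the 60 had the endoscopy in question (20 + 11 + 20). In those 51, p = 20/51, q = 31/51 and the result is 47.7%.
- Assumed p = q = 20%: 0.04 + 0.64 = 68%.

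The converse fails too. With sensitivity 100% and p = 1/3, accuracy of 50% means specificity (0.5 − 0.333) / 0.667 = 25%, and phi is then 0.32, which is a relation.

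**4. Effect on the test, n = 43, uninformative capsule.**

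- Correct versus incorrect against 50%, exact binomial. Success needs at least 29 of 43 (upper tail 0.0158, two-sided p = .032). A favourable result occurs in 0.6% of trials at the cited series' shares and in 1.6% where chance accuracy is 50%.
- Illustrations only: 60% at the assumed 20%/20%; 14% at shares inferred for the pre-market trial in section 2.2.5. There "30 consecutive patients with symptoms of acute UGIB were included; 28 were eligible for analysis", and the printed intervals suggest 6/28 and 10/28, with chance accuracy 58.2%. The implied specificity 18/22 is 81.8%, while the text prints 83%, so this reconstruction is not exact.
- Four equal cells, 3 df (simulation, 400,000 runs). At the cited shares p ≤ .05 occurs in 52% of trials. Observed accuracy is also above 50% in 14% of trials, and 75% or more in about 0.01%.

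**5. Adding a test of independence.** Requiring Fisher's exact test (two-sided .05, sensitivity + specificity > 1) as well lowers the 60% to 2.1% and the 14% to 1.8%. At sensitivity 100% and specificity 62.5%, the power of the combined rule stays 90.4% at 33% prevalence. At 21% prevalence it is 73.2% instead of 73.4%; the low figure there comes from accuracy itself falling to 71%.

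**The case against.** The strongest reply is that the plan can be read sensibly. Section 10.2 fixes accuracy at 50% against 75% or more, section 10.4.2 defines accuracy as the share of correct results, and n = 43 fits exactly that 1 df test. The alternative also shows the intended direction. This stands: a reader might infer that the primary test cannot be run at all, and that goes too far. The natural reading exists but is not stated, and the test named in sections 10.4.1 and 10.4.2 does not say it.

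A reader might also infer that w and n were taken from two different tests. The documents do not show this. One run at w = 0.62 with a wrong df of 5 would give 43 as well. Only the mismatch is established, not its origin.

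Third, the large error rates should not be read as the trial's expected false-positive rate. At the cited series' shares the accuracy test is conservative (0.6%). The 14% and 60% rest on inferred or assumed shares, and the 52% belongs to a four-equal-cell test that the plan never states. Sensitivity and specificity are calculated in any case, so an extreme failure such as a capsule that never signals would be visible.

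Finally, section 10.2 carries a footnote mark whose text is missing from the copy reviewed. The mark is on the sentence about the endpoint, not on the null hypothesis.

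**Conclusion.** The concern holds in three parts. The statement that 50% accuracy means no relation is wrong unless one of the two positive shares is 50%. The value w = 0.62 does not agree with n = 43 at alpha .05 and power .90 for 1, 2 or 3 df. The primary test lacks expected proportions and df, and no other document supplies them.

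n = 43 (50 enrolled) is supported for accuracy of 75% against 50%, with power 0.906 by chi-square or 0.904 by the exact test; nothing here says that 43 is too few. That power does not extend to sensitivity or specificity separately, nor does beating 50% show that either is adequate.

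How far accuracy could mislead depends on shares not yet known: no inflation at the cited series' shares, and substantial inflation only if both shares are low, which is an assumption. Because this is the only confirmatory test, the wording should be settled before the data are analysed.

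**What to change.** - **Section 10.2:** delete the clause that equates 50% accuracy with a random distribution and no relation. Keep 50% against 75%.
- **Sections 10.4.1 and 10.4.2:** state that the primary test compares correct with incorrect classifications against 50/50 (chi-square with 1 df, or its exact binomial equivalent, fixed in advance), two-sided .05, with success only if observed accuracy is above 50%. For the exact test this means at least 29 of 43, recomputed for the number analysed (33 of 50, for example).
- **Relation:** claim one only if Fisher's exact test is also met (two-sided .05, sensitivity + specificity > 1), since sections 3.1 and 4.2.1 make this the objective and endpoint.
- **Section 10.5:** replace w = 0.62 by w = 0.50 (1 df), keep 43 and 50, and limit the power statement to accuracy.
- **Reporting:** always give accuracy, sensitivity and specificity with exact 95% confidence intervals, beside the chance agreement from the observed shares.

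Cost: wording and a little more analysis, with no extra patients and almost no power (step 5). Choosing the exact test over chi-square is partly preference. It means that 28 of 43, significant by uncorrected chi-square (p = .047), no longer counts; its exact upper tail is 0.033, above .025. Accuracy alone could no longer be presented as evidence of a relation.

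### The stated alternative (accuracy of 75% or more) does not complement the 50% null, and the planned test does not examine 75%

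*Combined protocol and SAP*

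**What the plan says.** The combined protocol and SAP gives its hypotheses in section 10.2, for the primary endpoint only. The null reads: "The assumed null hypothesis is that the accuracy of the HemoPill acute measurement in comparison with endoscopic finding is 50" per cent, which the text equates with no relation between capsule and endoscopy. The alternative reads: "As the alternative hypothesis, it is assumed that the accuracy is equal or higher to 75" per cent. On the origin of that number the section adds: "This concrete accuracy value is derived from previous results".

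Sections 10.4.1 and 10.4.2 name one inferential procedure, a chi-square "goodness-of-fit test of a 2 x 2 contingency table with two tailed p-value of" 0.05 or less. Section 10.4.2 defines accuracy as true positives plus true negatives over all patients, and leaves 95% confidence intervals as something that may be computed after the test. Neither section contains a test against 75%, a criterion for a lower confidence limit or a minimum observed accuracy. Section 10.1 says there is no separate SAP.

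Section 10.5 uses the same 75% for sample size, with alpha 0.05 and power "equal or higher than .90", and arrives at 43 evaluable patients (50 enrolled).

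**The concern.** A null and an alternative should between them cover the values that the parameter can plausibly take, so that rejecting one has a clear meaning. Here they leave a gap from 50% to 75%. A test of 50% can show that accuracy differs from 50%. It cannot tell 60% or 70% from 75%. With H1 written as it is, someone following the usual logic of rejecting H0 in favour of H1 would take a significant result as support for 75% or more, a boundary that was never tested.

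This matters because the trial is meant to establish accuracy parameters (section 2.4.1) and its data are to help users interpret capsule readings (section 15.1). A conclusion pitched at the wrong level would carry into both uses.

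**Working it through.** **Inputs.** Null 50% and alternative 75% (section 10.2); two-sided alpha 0.05 (sections 10.4.1, 10.4.2, 10.5); power 0.90, 43 evaluable and 50 enrolled (section 10.5).

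**Where 75% comes from.** The multicentre series described in section 2.1 had 60 analysed patients: 20 capsule-positive with bleeding confirmed, 15 capsule-positive without a source found, and 25 capsule-negative. Counting all 25 negatives as correct, accuracy is (20 + 25)/60 = 75%, sensitivity 20/20 = 100% and specificity 25/40 = 62.5%. These match the figures in section 10.5. So 75% is an observed estimate used for planning.

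**Reproducing n = 43.** For a one-proportion chi-square test (df = 1) of 75% against 50%:

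- w = √[(0.75 − 0.50)²/0.50 + (0.25 − 0.50)²/0.50] = √0.25 = 0.50
- required n = (1.96 + 1.2816)²/0.50² = 10.51/0.25 = 42.03, rounded up to 43
- power at 43, with noncentrality 43 × 0.25 = 10.75, is 0.906

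This matches the planned number. The effect size printed in section 10.5, w = 0.62, does not: it gives 28 at df = 1 and 37 at df = 3. That mismatch is a separate matter and does not affect the result here.

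**Smallest result that rejects 50% at n = 43.** Chi-square = (x − 21.5)²/10.75.

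- x = 27 (62.8%): 30.25/10.75 = 2.81, p = 0.093, not rejected
- x = 28 (65.1%): 42.25/10.75 = 3.93, p = 0.047, rejected; Wilson 95% CI 50.2% to 77.6%

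The Wilson interval is the one that corresponds to the uncorrected chi-square test. With an exact binomial test, which the plan does not name, the cut-off moves to 29/43 = 67.4% (p = 0.032, exact CI 51.5% to 80.9%). If all 50 patients are evaluable, the chi-square cut-off is 32/50 = 64.0% (p = 0.048, Wilson CI 50.1% to 75.9%).

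Because the test is two-tailed, 15/43 = 34.9% gives the same statistic, (15 − 21.5)²/10.75 = 3.93. Read literally, an accuracy well below 50% would also reject H0 against an H1 of 75% or more.

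**How often 50% is rejected when true accuracy is below 75%** (n = 43, at least 28 correct):

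| True accuracy | Probability of rejection |
|---|---|
| 60% | 0.30 |
| 65% | 0.56 |
| 70% | 0.81 |
| 75% | 0.95 |

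**What it would take to exclude 75%.** For the Wilson lower limit to exceed 75%, x must exceed 43 × 0.75 + 1.96 × √(43 × 0.75 × 0.25) = 32.25 + 5.57 = 37.8, so 38/43 = 88.4%. With an exact interval it is 39/43 = 90.7%. The gap between 28 and 38 or 39 correct is the distance between what the test examines and what H1 states.

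**The case against.** The strongest reply is that this is shorthand. Planners often write the design value as the alternative. Section 10.2 says the 75% is assumed and comes from earlier results, section 10.5 uses it for power, and the study hypothesis in section 2.3.3 claims only adequate sensitivity and specificity. Accuracy itself will be calculated, so an observed 65% would appear as 65%.

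Much of this stands. A reader might infer that the protocol plans to announce accuracy of at least 75% whenever the test is significant. The documents do not support that: no section says so. What remains is that the section headed as the hypotheses gives 75% or more as H1, nothing elsewhere limits what rejection means, and the interval that would expose the limit is optional.

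A second reply is that the 65% cut-off depends on how an ambiguous test is read. That is correct. Section 10.4 speaks of a goodness-of-fit test of a 2 x 2 table, and section 10.5 applies it to sensitivity and specificity as well. As a comparison with four equal cells (df = 3), 29/43 correct need not reject: cells of 14, 7, 7 and 15 give (3.25² + 3.75² + 3.75² + 4.25²)/10.75 = 5.28, p = 0.15. As a test of association, there is no fixed accuracy cut-off. But neither alternative reading tests 75%, so the mismatch with H1 remains; only the size given above is tied to the df = 1 reading.

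**Conclusion.** The point holds as a defect in how the hypotheses are stated and in what the planned test can support. H0 and H1 are not complementary, and 75% is a planning value that no planned analysis tests. On the df = 1 reading, which fits the null in section 10.2 and reproduces n = 43, H0 is rejected from 65% correct, with an interval running from just above 50% to about 78%. At true accuracies of 65% to 70% that happens in 56% to 81% of trials. These sizes assume 43 evaluable patients and an uncorrected chi-square test; the true accuracies are illustrative assumptions.

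It does not follow that the sponsor intends a claim of at least 75%, nor that the sample size is wrong for testing 50%. The risk lies in how a significant result may be interpreted, and it can be removed by wording.

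**What to change.** Rewrite the second paragraph of section 10.2 as H0: accuracy = 50%, H1: accuracy different from 50%, favourable if above. Move 75% out of the hypotheses and name it as the planning value in section 10.5 only. Add one sentence saying that rejection in the favourable direction supports accuracy above 50% and nothing further. In section 10.4.2, make the 95% confidence interval for accuracy mandatory, name its method (Wilson if the uncorrected chi-square test is kept), and state that any remark about 75% rests on that interval alone.

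This changes no procedure, data item or sample size. The cost is a more modest permitted claim.

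If the sponsor does want to claim at least 75%, rewording is not enough: the test would have to be against 75% and the trial resized. By normal approximation (two-sided 0.05, 90% power) that needs about 171 evaluable patients if true accuracy is 85% and about 68 if it is 90%. Both true values are assumptions, not figures from the protocol.
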